7.1 Assessments Related to the Primary Endpoint

7.1.1 Pharmacokinetics

Blood samples for measurement of plasma concentration of diclofenac will be collected on the 1st and 7th day of treatment (Days 1 and 7). Samples will be collected pre-dose (within 1 hour) and 2 (± 15 min), 4 (± 15 min), 6 (± 15 min), 8 (± 15 min), 10 (± 15 min), 12 (± 15 min), 14 (± 15 min), 16 (± 15 min), 18 (± 15 min), 20 (± 15 min), and 24 (± 30 min) hours post initial application (Day 8). One blood sample will be collected on the 3rd, 4th, 5th, and 6th day of treatment (Days 3, 4, 5, and 6). These samples will be collected within 1 hour prior to dosing in the morning. At the end of Period 3, there will be three additional PK blood samples taken respectively at 3 weeks (21 days), 4 weeks (28 days), and 5 weeks (35 days) after the last application of IMP (see [Table 2](#)).

Specific instructions on sample handling will be described in the laboratory manual provided by the bioanalytical laboratory. Samples will be split into two aliquots: one aliquot for analysis (with sufficient material to allow for a repeat analysis at the bioanalytical laboratory) and one aliquot remaining at the clinical site to serve as a backup sample. Samples will be shipped frozen to the bioanalytical laboratory for analysis. A validated liquid chromatography-tandem mass spectrometry (LC-MS/MS) method with an LLOQ of 50 pg/mL for the analysis of diclofenac will be employed for sample analysis, as described in a sample analysis plan.

7.2 Other Assessments

7.2.1 Vital Signs

Vital signs comprising systolic and diastolic arterial blood pressure, pulse and body temperature will be assessed at screening, Day -1, and Day 8 visits. Systolic and diastolic blood pressure will be measured after the subject has been in seated or supine position for at least 1 minute. All recordings will be performed using standard equipment.

Clinically significant abnormal findings will be reported as adverse events (AEs).

7.2.2 Laboratory Parameters

7.2.2.1 Clinical Safety Laboratory Tests

Blood samples for clinical chemistry, hematology and urinalysis will be collected at screening and on Day 8. Laboratory safety evaluations will be performed according to [Table 3](#) below. The clinical chemistry, hematology and urinalysis will be performed by a diagnostic laboratory.

Clinically significant abnormal findings will be reported as AEs.

Table 3 - Safety Laboratory Parameters

| Clinical Chemistry | Hematology | Urinalysis |
|---|--|--------------|
| Alanine aminotransferase | Hematocrit | Protein |
| Alkaline phosphatase | Hemoglobin | Glucose |
| Aspartate aminotransferase | Platelet count | Bilirubin |
| Calcium | Red blood cell count | pH |
| Cholesterol | Reticulocytes | Nitrite |
| Creatinine | White blood cell count with differential | Ketone |
| Gamma-glutamyl transferase | Monocytes, large unclassified cells | Urobilinogen |
| Glucose | | Blood |
| Potassium | | Leukocytes |
| Sodium | | |
| Total bilirubin | | |
| Triglycerides | | |
| Urea (blood urea nitrogen) | | |
| SPT (screening only) | | |
| Serology: HIV, HBsAG, and HCV test (screening only) | | |

7.2.3 Physical examination

Physical examination will be performed at the screening, Day -1, and Day 8. Clinically significant abnormal findings at follow-up will be reported as AEs.

A full physical examination will include an evaluation of the head, eyes, ears, nose, throat, neck, heart, chest, lungs, abdomen, extremities, skin, and any other notable conditions.

7.2.4 12-Lead Electrocardiogram (ECG)

A standard bedside 12-lead ECG will be recorded using the study site's own ECG equipment and will be evaluated by the Investigator.

7.2.5 Administration Site Reactions

The skin at the application site will be examined by the Investigator or designee (see [Section 6.2](#) for when examinations will take place). The skin tolerability will be documented in the eCRF according to the terminology of the International Contact Dermatitis Research Group:

- 0 no reaction (negative documentation)
- 1 doubtful reaction
- 2 mild erythema
- 3 strong erythema
- 4 very strong erythema and edema

These administration site reactions will be recorded in an eCRF page dedicated to dermal findings. Mild, strong, and very strong erythema and edema (skin tolerability score ≥ 2) will be reported as AEs.

7.3 Handling of Biological Samples

A detailed description of all sample collections and shipment procedures will be included in a separate laboratory manual.

7.4 Laboratory Values

The Investigator will review the laboratory test results, evaluate, and document whether the results are non-clinically or clinically significant.

8. ADVERSE EVENTS

8.1 Adverse Event (AE) Definition

An AE is any untoward medical occurrence in a subject participating in a clinical study. It includes:

- Any unfavorable and unintended sign, symptom or disease temporally associated with the use of the IMP, whether or not considered to be caused by the IMP.
- AEs commonly observed, and AEs anticipated based on the pharmacological effect of the IMP.
- Any laboratory abnormality, vital sign or finding from physical or other examinations assessed as clinically significant by the Investigator [Note: findings from assessments and examinations done during screening are not AEs but are recorded as medical history.]
- Accidental injuries, reasons for any change in medication (drug and/or dose), reasons for any medical, nursing or pharmacy consultation, or reasons for admission to hospital or surgical procedures.

- Overdoses and medication errors with and without clinical consequences.

All pre-treatment events will be captured as medical history.

A treatment emergent AE (TEAE) is defined as any AE occurring after start of IMP administration and within the time of residual drug effect (5 days), or a pre-treatment AE or pre-existing medical condition that worsens in intensity after treatment with the IMP and within the time of residual drug effect.

A post-treatment AE is defined as any AE occurring after the first dose of study drug and until the last study visit (end-of-study visit) or until 3 weeks post dose (whichever is longer).

8.2 Collection and Recording of Adverse Events

8.2.1 Collection of Adverse Events

The Investigator must monitor the health of the subject throughout the study from the time of enrolment until the last study visit.

The sources of AEs cover:

- The subject's response to questions about his or her health (a standard non-leading question such as "How have you been feeling since your last visit?" is asked at each visit).
- Symptoms spontaneously reported by the subject.
- Investigations and examinations where the findings are assessed by the Investigator to be clinically significant changes or abnormalities.
- Other information relating to the subject's health becoming known to the Investigator (e.g., hospitalization).

8.2.2 Recording of Adverse Events

The Investigator must record all AEs in the AE Log provided in each subject's eCRF with information about:

- AE
- Date and time of onset (time can be omitted, if applicable)
- Intensity
- Causal relationship to IMP
- Action taken with IMP.
- Other action taken.

- Date and time of outcome (time can be omitted, if applicable)
- Outcome
- Seriousness

Each of the items in the AE Log is described in detail in the following sections.

Adverse Event

Adverse events should be recorded as diagnoses, if available. If not, separate signs and symptoms should be recorded. One diagnosis/symptom should be entered per record.

If a subject suffers from the same AE more than once and the subject recovers in between the events, the AEs should be recorded separately. If an AE changes in intensity, a worst-case approach should be used when recording the event, i.e., the highest intensity and the longest duration of the event. *Exception: If a symptom or diagnosis with onset before the first IMP administration (i.e., a pre-treatment event) increases in intensity, this must be recorded as AE. The initial symptom or diagnosis should be recorded as medical history. While AE should be reported with date/time of onset when the intensity increased.*

Note: A procedure is not an AE; the reason for conducting the procedure is. Hospitalization is not an AE; the reason for hospitalization is. Death is not an AE, but the cause of death is (an exception is sudden death of unknown cause, which is an AE).

Date and Time of Onset

The date of onset is the date when the first sign(s) or symptom(s) were first noted. If the AE is an abnormal clinically significant laboratory test or outcome of an examination, the onset date is the date the sample was taken, or the examination was performed.

Intensity

The intensity of an AE must be classified using the following 3-point scale:

- | | |
|-----------|--|
| Mild: | Awareness of signs or symptoms, but no disruption of usual activity. |
| Moderate: | Event sufficient to affect usual activity (disturbing). |
| Severe: | Inability to work or perform usual activities (unacceptable). |

Causal Relationship to IMP

The possibility of whether the IMP caused the AE must be classified as one of the following:

Reasonable possibility:

There is evidence or argument to suggest a causal relationship between the IMP and the AE. The AE may occur as part of the pharmacological action of the IMP or may be unpredictable in its occurrence.

Examples:

- adverse events that are uncommon but are known to be strongly associated with IMP exposure.
- adverse events that are not commonly associated with IMP exposure, but the event occurs in association with other factors strongly suggesting causation, such as a strong temporal association or the event recurs on rechallenge.

No reasonable possibility:

- There is no reasonable evidence or argument to suggest a causal relationship between the IMP and the AE.

Examples:

- known consequences of the underlying disease or condition under investigation.
- adverse events common in the study population, which are also anticipated to occur with some frequency during the course of the study, regardless of IMP exposure.

Action Taken with IMP

The action taken with the IMP in response to an AE must be classified as one of the following:

- No change (medication schedule maintained or no action taken)
- Withdrawn
- Interrupted

Other Action Taken

Adverse events requiring therapy must be treated with recognized standards of medical care to protect the health and well-being of the subject. Appropriate resuscitation equipment and medicines must be available to ensure the best possible treatment for an emergency situation.

If medication is administered to treat the AE, this medication should be entered in the eCRF.

Date and Time of Outcome

The date and time (time can be omitted, if applicable) the subject recovered or died. If outcome is “Not recovered” or “Recovering” no date of outcome can be recorded.

Outcome

The outcome of an AE must be classified as one of the following:

- Recovered (fully recovered or the condition has returned to the level observed at initiation of study treatment)
- Recovered with sequelae (resulted in persistent or significant disability/incapacity)
- Recovering
- Not recovered
- Fatal

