10.6 Safety Evaluations

Adverse Events

Adverse event terms will be coded using the MedDRA version 25.1 (2022) dictionary. All AEs will be presented in a by-subject listing, detailing the verbatim term given by the investigator, the preferred term (PT), system organ class (SOC), onset date and time, end date and time, intensity, outcome, relationship to study drug, action taken with study drug, other action taken, seriousness and criteria for seriousness. A separate listing for any serious adverse events and adverse events Leading to study discontinuation will also be provided.

A summary table of treatment-emergent adverse events (TEAE) will be presented including for each treatment the number of subjects reporting an AE, the percentage of subjects with an AE, and the number of events reported, for the following categories: all AEs, severe AEs, serious AEs (SAEs), adverse drug reactions (ADRs, defined as AEs considered by the Investigator to be at least possibly related to the study drug), AEs leading to subject withdrawal, and deaths. For the purpose of the summary, each AE will be counted according to the most recently applied treatment at the time of onset.

Missing values will be treated as missing except for causality, intensity, seriousness, and outcome of an AE, at which occurrence a “worst case” approach will be taken. Thus, if causality is missing the AE will be regarded as related to the study drug, if the intensity is missing the intensity of the AE will be regarded as severe, if seriousness is missing the AE will

be regarded as an SAE, and if the outcome is missing and no date of outcome is present the outcome is regarded as “Not Recovered.”

Vital Signs

Blood pressure, heart rate (pulse), and body temperature will be recorded at Screening, Day –1 pre-dose of each treatment period, and Day 8 of each treatment period. These values will be reported in by-subject listings and summarized by time point as well as change from Day –1 to Day 8 as mean, standard deviation, minimum, and maximum.

Physical Examination

Complete physical examinations will be performed at Screening, Day –1 pre-dose of each treatment period, and Day 8 of each treatment period. The results of these examinations will be presented in by-subject listings.

Administration Site Reactions

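### An adverse event still unresolved when the next product starts, and worsening under it, would be counted at its worst intensity under the earlier product and not under the later one

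*Protocol*

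**What the plan says.** Protocol 8.2.2 sets the recording rules:

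- A change in severity does not open a new entry: "If an AE changes in intensity, a worst-case approach should be used when recording the event, i.e., the highest intensity"; duration is treated the same way.
- Onset is fixed at the start of the event: "The date of onset is the date when the first sign(s) or symptom(s) were first noted".
- One case is carved out. If a condition "with onset before the first IMP administration (i.e., a pre-treatment event) increases in intensity, this must be recorded as AE". That entry is dated from the increase in intensity.
- An event that clears and returns is not affected. Where "the subject recovers in between the events, the AEs should be recorded separately".

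Each entry in the AE log has one item each for intensity, causality, action taken and seriousness.

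SAP 10.6 sets the counting rule for the summary by treatment: "each AE will be counted according to the most recently applied treatment at the time of onset". That summary covers all AEs, severe AEs, SAEs, ADRs, AEs leading to withdrawal and deaths. Protocol 9.7.6.2 adds tables per treatment by causality and by intensity.

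Protocol 8.1 limits treatment-emergent events to a residual-effect window of 5 days, and adds a worsening clause: "or a pre-treatment AE or pre-existing medical condition that worsens in intensity after treatment with the IMP". Protocol 9.7.6 tabulates treatment-emergent events only and lists the others.

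**The concern.** The recording rules suit a trial in which each subject gets one product. Here each subject gets three in turn. The protocol accepts that a worsening after dosing should be dated from the worsening, so that it counts against the drug. It applies this only to events that began before any study product was given. An event that began under or after the first product and worsened under the second has no such provision.

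Comparing the safety and tolerability of the three products is a secondary objective, reported as counts per treatment. Severe events, serious events and withdrawals are likely to be sparse in healthy subjects, so a single event in the wrong column can be visible in those rows.

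**Working it through.** The plan states no figure on this point. The check is to follow one event through the rules, then ask how often the conditions could be met and whether the design gives a direction.

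**1. Tracing one event.** Take Sequence 5 (A, then C, then B; SAP Section 3). A mild event begins in Period 1 under A, does not resolve, and becomes severe in Period 2 under C, where it leads to withdrawal.

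| Step | Rule | Result |
|---|---|---|
| New entry at worsening? | Protocol 8.2.2: exception only for onset before the first study product | No; one entry |
| Intensity | Protocol 8.2.2: highest reached | Severe |
| Onset | Protocol 8.2.2: first sign | Period 1 |
| Action taken, seriousness | One item per entry | Withdrawn; serious, if it became so |
| Column in the table | SAP 10.6: last product at onset | A |
| Entry under C | None | Zero |

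Causality is less clear. The worst-case rule names intensity and duration, not causality. If A caused the onset, an ADR under A is correct and only C's contribution is lost. The ADR is wrongly placed only if the single causality rating was given because of what happened under C.

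**2. Onset during washout.** Such an event needs to persist only until the next period starts. SAP 10.6 still points to the earlier product. If it began more than 5 days after the last dose, it is outside the Protocol 8.1 window at onset, and the tables may omit it. If the worsening clause is read to cover it, it becomes treatment-emergent but its onset date does not move. On either reading nothing is counted under the later product.

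**3. How often.** All of these must hold: onset after the first dose and before Period 3 dosing starts, no recovery before the next product, continuation into the next period, and worsening there. The documents give no AE durations. As an illustration, assume exponential durations with mean *m*. The chance that an event present at the last dose lasts a gap of *g* days is exp(−*g*/*m*):

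| Assumed mean *m* (days) | *g* = 21 | *g* = 28 |
|---|---|---|
| 3 | exp(−7) = 0.1% | exp(−9.33) = 0.01% |
| 7 | exp(−3) = 5.0% | exp(−4) = 1.8% |
| 14 | exp(−1.5) = 22.3% | exp(−2) = 13.5% |
| 30 | exp(−0.7) = 49.7% | exp(−0.933) = 39.3% |

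These are chances of persistence only; the event must then also worsen. They do not cover onset during washout, where the gap is shorter.

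With 75 randomised and no dropout, 75 × 2 = 150 of 75 × 3 = 225 subject-periods follow another product. That is where the rule could apply, not a count of affected events.

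**4. Direction.** Six sequences × 2 changes = 12 changes of product. Each of the six ordered pairs (A→B, B→A, A→C, C→A, B→C, C→B) occurs twice. The design therefore favours no product, although the errors need not cancel if AE rates differ between products.

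**The case against.** The strongest reply is that the event is rare and much of the safety record does not depend on it.

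- **Washout and eligibility.** The washout is at least 21 days. Day -1 is repeated before Periods 2 and 3, with eligibility criteria, physical examination and treatment-area assessment (Protocol 6.2.2). Exclusions 1 and 13 cover knee lesions and clinically significant laboratory values. This stands as a reason to expect few events. It does not close the gap: no passage requires an AE to have resolved before the next period, and Protocol 8.5.1 allows follow-up to end once the condition is stable.
- **Skin reactions.** Scores are taken daily and summarised by treatment, by day and as worst score (SAP 10.6). A skin reaction that worsens under a later product appears there. This stands, although scores of 2 or more also become AEs (Protocol 7.2.5), and other kinds of event have no such second record.
- **Visibility.** Safety is descriptive, and listings by subject show dates, intensity and action taken. A listing would show a long event, but one entry at its worst intensity does not show when it worsened.
- **Other documents.** The Safety Management Plan and the eCRF instructions are not available here and might deal with this. That remains open.

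Some stronger readings are tempting. A reader might infer that a worsening under the second or third product can never be counted against it. That is not so: the exception turns on onset, so a pre-treatment condition that worsens in Period 2 or 3 is dated from the worsening and counted under that product. A reader might also infer that every unresolved event is misplaced, but one that does not worsen is counted correctly. Nor do the rules misassign relatedness in general.

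**Conclusion.** The gap is real and follows from the two documents read together; the recording sentence alone does not create it. It is conditional and narrow. It affects events that start after the first dose, in a treatment period or in washout, are unresolved when the next product starts, and then worsen. For those, intensity is misplaced, as is any serious or withdrawal outcome arising under the later product. Relatedness is misplaced only if the causality rating reflects the later product.

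The number cannot be estimated from the documents and should be small. The persistence table rests on assumed durations and is illustrative only. No fixed direction of bias is claimed. The primary PK comparison is unaffected. The correction is worth making because the affected rows are likely to be sparse and the change is cheap.

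**What to change.** **Protocol 8.2.2.** Apply the single worst-case record only within a treatment period, and extend the existing exception. If an AE is ongoing at the first application of a later period and then increases in intensity or becomes serious, enter a new linked record. Date its onset from the worsening and give it its own intensity, causality, seriousness and action taken. The earlier record keeps the intensity it had before the worsening.

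**SAP 10.6.** Count the new record as treatment-emergent, under the product being applied when the worsening occurred. This also settles events that began in washout outside the 5-day window.

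**Cost.** One sentence in each document, and a worsening date and extra entry for each such event. AEs are reviewed daily during confinement (Protocol Table 1), so the date should be obtainable. The event count rises slightly because one event becomes two linked records; a footnote to the table can say so. This changes recording and counting only, not clinical management.

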8.3 Pregnancy and Pregnancy Outcome

If a pregnancy occurs in female subjects, the IMP should be immediately stopped, and the subject must be withdrawn from the study (as pregnancy is an exclusion criteria). TKL will inform Amzell B.V. including information about contact details for the follow-up on the course and outcome of the pregnancy. The pregnancy must be followed-up at least until the birth of the infant and one month after the birth of the infant. In general, the follow-up will include the course, duration, and the outcome of the pregnancy as well as neonatal health. If a pregnancy results in an abnormal outcome (birth defect/congenital anomaly) TKL will report this as a serious AE to Amzell B.V.

8.4 Serious Adverse Events

8.4.1 Serious Adverse Event (SAE) Definition

| An event is defined a serious adverse event if it: | Guidance |
|--|---|
| results in death | Any event resulting in a fatal outcome must be fully documented and reported, including deaths occurring within four weeks after the treatment ends and irrespective of the causal relationship to the IMP. The death of a subject enrolled in a study is per se not an event, but an outcome. |
| is life-threatening | The term life-threatening refers to an AE in which the subject was at immediate risk of death at the time of the event. It does not refer to an event, which may have caused death if it were more severe. |
| requires in-patient hospitalization or prolongation of existing hospitalization | The term hospitalization means that the subject was admitted to hospital, or that existing hospitalization was extended as a result of an event. Hospitalization describes a period of at least 24 hours. An overnight stay for observation, stay at emergency room or treatment on an out-patient basis do not constitute a hospitalization. However, medical judgment must always be exercised and when in doubt the case should be considered serious (i.e., if the case fulfills the criterion for a medically important event). Hospitalizations for administrative or social purposes do not constitute an SAE. Hospital admissions and/or surgical operations planned before study inclusion are not considered AEs, if the illness or disease existed before the subject was enrolled in the study, provided that the condition did not deteriorate during the study. |
| results in persistent or significant disability/incapacity | Disability/incapacity means a substantial disruption of a person's ability to conduct normal life functions. In doubt, the decision should be left to medical judgment by the Investigator. |
| is a congenital anomaly/birth defect | Congenital anomaly/birth defect observed in any offspring of the subject conceived during treatment with the IMP. |

| An event is defined a serious adverse event if it: | Guidance |
|--|--|
| is an important medical event | 
Important medical events are events that may not be immediately life-threatening or result in death or hospitalization but may jeopardize the subject or may require intervention to prevent one of the other outcomes listed in the definition above. Examples of important medical events include AEs that suggest a significant hazard, contraindication or precaution, occurrence of malignancy or development of drug dependency or drug abuse. Medical and scientific judgment should be exercised in deciding whether events qualify as medically important.
 
Important medical events include any suspected transmission of an infectious agent via a medicinal product. Any organism virus or infectious particle (e.g., prion protein transmitting Transmissible Spongiform Encephalopathy), pathogenic or non-pathogenic, is considered an infectious agent. A transmission of an infectious agent may be suspected from clinical symptoms or laboratory findings indicating an infection in a subject exposed to a medicinal product.
 |

